The CDC estimates that approximately 10% of the US population will experience a seizure and 3% will be diagnosed with recurrent seizures (epilepsy) before age 80. Unfortunately, diagnosing epilepsy is often a long, costly, and challenging process involving a combination of a physician's clinical impression, electroencephalogram (EEG), magnetic resonance imaging (MRI) and, where available, a multiday inpatient test that combines closed circuit TV and EEG (CCTV/ EEG monitoring). Due to both the high cost and complexity of diagnosis, approximately 30% of patients who are treated by a neurologist for epilepsy are actually experiencing events from other causes, such as syncope, transient ischemic attack, or psychiatric disorder.¹ A rapid, cost-effective, and accurate blood test for epilepsy would allow clinicians to prescribe treatment quickly for patients who test positive and to redirect the workup on patients who test negative. While there have been many previous efforts to find such a blood test, including tests of hormone concentrations such as prolactin and tests of brain tissue breakdown such as neuron specific enolase,^{2,3} these have not had a high enough sensitivity or specificity for epilepsy to be of clinical value.

Recent studies have established that brain inflammation is a prevalent etiological process factor in focal epilepsies, and may contribute to seizure generation.⁴ Levels of pro-inflammatory cytokines are increased in epilepsy surgical pathology specimens, which likely elevate levels of excitatory neurotransmitters and impair neuronal inhibition, increasing the likelihood of seizures.⁵ Further, blocking this inflammation reduces or prevents seizures in preclinical models.⁶

Consistent with this research, investigators at the University of Pennsylvania have identified a potential diagnostic blood test for epilepsy called the CNS-specific Assay for Recurrent Paroxysmal Events (CARPE), which is defined as the ratio of the plasma concentrations of two lymphocytic regulatory proteins: TARC and sICAM5. The CNS-specific component of this test is the soluble fraction of Intracellular Adhesion Molecule 5 (sICAM5), a protein that likely originates in the CNS. Preliminary data show that anti-inflammatory sICAM5 concentrations are consistently low in epilepsy patients. The second component of the test is Thymus and Activation Regulated Chemokine (TARC or CCL17), a lymphocyte chemoattractor that in preliminary data was present in consistently high concentrations in epilepsy patients. In contrast with the T-cell inhibitory function of sICAM5, TARC binds specifically to CCR4 receptors on T-cells and induced chemotaxis in T-cell lines. TARC is known to be principally expressed peripherally in blood mononuclear cells and the thymus.^{7,8} The origin of the high concentrations of TARC found in patients with seizures is not known and could arise either systemically or within the central nervous system. Nonetheless, TARC concentrations are high in patients with seizures, consistent with a pro-inflammatory process.

The present study is designed to establish the accuracy of CARPE as a diagnostic tool for epilepsy in an outpatient neurology clinic, the population that would most immediately benefit from such a test. Exploratory goals include determining whether additional cytokines and chemokines may enhance CARPE's accuracy, determining whether levels of sICAM5 or other cytokines or chemokines predict or confirm subjects' responses to antiepileptic drugs (AEDs), and determining the degree to which CARPE's accuracy is temporally related to seizures or seizure-like events.

2 Study Design

Specific Aim 1: To establish the accuracy of the CARPE blood test for determining the presence of epilepsy, and in doing so, establish the threshold for diagnosis

- a. Hypothesis: CARPE will accurately identify greater than 70% of patients as epileptic
- b. Method 1a: Enroll a total of 240 Research Subjects aged 12 and older who have been referred to the University of Pennsylvania's Penn Epilepsy Center for diagnostic evaluation and have a subsequent workup at Penn or an outside site that includes an EEG. All subjects will be asked to provide a single sample of blood for CARPE testing and allow the study team to review their medical records and collect information about their epilepsy diagnosis. Subjects who enroll and do not give a blood sample and have an EEG that is available for study review will be replaced. Analyzed subjects' clinically indicated work-up must include an EEG, and additional diagnostic tests will be at the discretion of the subjects' physicians. After six months of clinical care, an independent panel of three epileptologists will review the subjects' medical records and determine each subject's diagnosis. The study team will compare the panel's diagnoses with the CARPE results
- c. Method 1b: Collect up to two 5ml tubes of blood via a single venipuncture from a maximum of 240 individuals aged 18 and over who accompany patients to their Penn Epilepsy Center appointments as true controls. To be eligible, Control Subjects must confirm that they have not been diagnosed with epilepsy and that they are not taking any medications used to treat epilepsy, and they will be asked to sign a separate Informed Consent Form. As explained in the ICF, the study team will not collect any PHI from Control Subjects; information collected will be limited to the following data points at the time of consent: age, gender, presence of an epilepsy diagnosis, and whether they are taking any medications used to treat epilepsy (potential subjects will be provided with a comprehensive list with brand and generic medication names to review).

Specific Aim 2: As an exploratory endpoint, we will determine whether additional cytokines and chemokines may enhance the accuracy of the CARPE

Specific Aim 3: As an exploratory endpoint, we will determine whether CARPE's diagnostic accuracy is temporally related to time of last seizure

- a. Hypothesis: CARPE's accuracy decreases as more time elapses between the seizure or seizure-like event and sample collection
- b. Method: Collect postictal blood samples from Research Subjects aged 12 and older who have been referred to the University of Pennsylvania for continuous video EEG (cVEEG) monitoring. Subjects will be asked to provide a single sample of blood for CARPE testing per day and up to one additional blood sample per day (12:00am-11:59pm) if the subject experiences a seizure or seizure-like event while undergoing cVEEG.

We will use clinical determination as the gold standard for classifying the event.

Specific Aim 4: As an exploratory endpoint, we will determine whether levels of sICAM5 or other cytokines or chemokines predict or confirm AED efficacy

- a. Hypothesis: CARPE levels will distinguish Research Subjects who achieve seizure freedom, defined seizure freedom since treatment change
- b. Method: Research Subjects who join the study will have the option of providing a sample of blood for research at any regularly scheduled clinic visit that takes place during the 12 months after enrollment

3 Subject Selection, Enrollment, & Withdraw

3.1 Vulnerable Populations

Fetuses, neonates, and prisoners are not eligible to participate. Pregnant women will not be targeted but will not be excluded, provided that they have not given, and are not expected to give, blood for any other reason within one week of the study. Children under 12 are excluded; children aged 12-17 must provide assent if they are mentally capable of doing so, and must also have a caregiver provide Informed Consent on their behalf.

Potential Control Subjects must be able to provide consent on their own behalf. Research Subjects who are unable to consent for themselves, including those who are institutionalized, are eligible provided that they do not express any objections and a Legally Authorized Representative (LAR) signs Informed Consent on their behalf. Inclusion of individuals who are unable to provide informed consent is based on the principle of beneficence: approximately 25% of epilepsy patients fall into this category, and they are well-represented in the group that may ultimately benefit from this test. In all cases, every effort will be made to inform both the potential subject and the healthcare representative of the study and the associated risks and benefits.

Any member of the following classes, who is reasonably available, may act as a subject's healthcare representative (in descending order of priority):

- Spouse (unless an action for divorce is pending)
- Adult child (18 years or older)
- Parent
- Adult sibling
- Adult grandchild
- Other adult who has knowledge of the patient's preferences and values, including but not limited to religious and moral beliefs, who assess how the patient would make decisions

3.2 Inclusion Criteria

3.2.1 Research Subjects

- Aged 12 and older
- Evaluation in at least one of the following settings:
 - Newly referred to the University of Pennsylvania's Penn Epilepsy Center. These patients may not have completed any diagnostic evaluation at Penn, other than an initial physician consultation,

prior to enrollment and must agree to allow the study team to collect records regarding their diagnostic evaluations (including EEG). Diagnostic evaluations may take place at Penn or outside sites

- All patients who are admitted to the University of Pennsylvania for cVEEG monitoring

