3.3.1 Research Subjects

- Patients who, in the opinion of the investigator or the patient's neurologist, are unable to give Informed Consent due to mental impairment or any other reason AND do not have a LAR who can give Informed Consent on their behalf. Patients aged 12-17 (inclusive) must provide assent if they are mentally capable of doing so, and must also have a caregiver who provides Informed Consent on their behalf
- Patients who, in the opinion of their neurologist at the University of Pennsylvania, are not good candidates for donating blood for any reason

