3.3.2 Control Subjects

- Younger than 18
- Experience seizures or suspected seizures of any type (a single instance of febrile seizure prior to age 2 is allowed)
- Treatment with an anti-seizure medication within two months prior to providing a blood sample
- Unable to provide Informed Consent

3.4 **Recruitment**

Before the research begins, the Principal Investigator will present this study to the University of Pennsylvania's Neurology Department's Patient-Oriented Research Committee.

The study team will also present the study to the attending epileptologists, resident physicians, fellows, and nurse practitioners at the Penn Epilepsy Center and ask for their advance permission to contact their new patients in the outpatient clinic, and their patients who are admitted to HUP for cVEEG monitoring. Physicians who object to the study for any reason may elect not to allow their patients to participate. Physicians and nurse practitioners may also elect to contact the study team to prohibit them from inviting individual patients to join for any reason, or to prohibit enrolled subjects from giving blood. All Research Subjects who join the study at their first outpatient visit may provide a blood sample in support of Specific Aim 1, regardless of when the blood draw occurs – at their first visit or at a later visit – since they will have been prospectively identified and enrolled as part of a true cohort.

In the interest of enrolling a true cohort and in consideration of the low-risk nature of this study, in the absence of an attending physician's objection, the study team may approach all potentially eligible patients (provided that the physician has previously approved the study as described above).

The study team will review clinic lists and identify patients who are attending new outpatient visits at the Penn Epilepsy Center or are being admitted for cVEEG monitoring. A member of the study team may approach and consent any potential subject in the outpatient setting at any point during their visit. The study team may approach any potential subject who has been admitted for cVEEG monitoring at any point after his or her admission.

The study team will invite adults who accompany Research Subjects to participate as Control Subjects as time permits until a maximum of 240 Control Subjects have provided a single blood sample.

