All data will be stored in study binders, separate from signed Informed Consent/ HIPPA forms.

7 Data Analysis

7.1 *Sample Size Determination*

Enrollment will continue until 240 outpatients have joined the study, provided a single blood sample, and undergone an EEG that is accessible to the study team. Subjects who either do not provide a blood sample or do not undergo an EEG will be replaced.

This sample size is based on the need for 68 subjects per group and reflects the expectation that within six months of initial presentation, 50% will be diagnosed with epilepsy, 30% will be diagnosed with non-epileptic events, and 20% will have an unknown diagnosis.

Control samples will be used as needed to further validate the CARPE test.

7.2 *Statistical Methods*

The goals of the study are to determine whether the CARPE value can be used effectively and accurately to diagnose patients with epilepsy, and to establish the threshold for diagnosis. The CARPE AUC from

the ROC curve of our pilot data was 1.0 and the sICAM5 AUC was 0.87. For a conservative estimate, the sample size will be estimated based on the sICAM5 AUC, which is the lower value.

Accuracy: To determine the accuracy of the test, we will construct ROC curves for sensitivity and specificity of CARPE by varying the threshold value for classifying epilepsy patients. The gold standard for constructing the ROC curve will be the diagnosis as determined by the panel of three independent epileptologists. The aim of this part of the study is to construct a reliable ROC curve. It is likely that the gold standard panel will not come to a conclusive diagnosis approximately 20% of the time, and these unknowns will not be included in the ROC determination. We will consider a conclusive diagnosis to be agreement between at least two of the three epileptologists that the subject is epileptic or non-epileptic at the time of evaluation. We use the AUC of the ROC curve as a global measure of the effectiveness of these measurements. To this end, we assume that the prevalence rate is 50% for epilepsy among all the study subjects. Moreover, we assume that the CARPE and sICAM5 measures are normally distributed for both epilepsy and non-epilepsy subjects.

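### The eligibility and counting rules do not carry over Aim 1's restriction to patients referred for diagnosis, so patients with a settled diagnosis can enter the deciding AUC, with a bias of unknown direction

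*Combined protocol and SAP*

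**What the plan says.** The Aim 1 population is defined in Section 2, Specific Aim 1, Method 1a. Subjects are those "referred to the University of Pennsylvania's Penn Epilepsy Center for diagnostic evaluation and have a subsequent workup at Penn or an outside site", and that workup must include an EEG.

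The rules that staff apply when they screen and count are wider:

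- **Section 3.2.1** takes patients who are "Newly referred to the University of Pennsylvania's Penn Epilepsy Center. These patients may not have completed any diagnostic evaluation at Penn" beyond a first consultation. It adds: "Diagnostic evaluations may take place at Penn or outside sites". It gives no reason for referral and sets no limit on evaluation already completed elsewhere.
- **Section 3.3.1** has two exclusions: inability to consent without a representative, and patients who in their neurologist's view "are not good candidates for donating blood for any reason". Neither an existing diagnosis nor current anti-seizure treatment excludes a patient.
- **Section 3.4** has the team review clinic lists and "identify patients who are attending new outpatient visits at the Penn Epilepsy Center", with no filter on the referral question.
- **Section 7.1** sets the count: "Enrollment will continue until 240 outpatients have joined the study, provided a single blood sample, and undergone an EEG that is accessible". It does not say when the EEG must have been done. The planning split is for diagnoses made soon after presentation: "within six months of initial presentation, 50% will be diagnosed with epilepsy, 30% will be diagnosed with non-epileptic events", with the remaining 20% unknown.

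Section 7.2 makes the comparison of the AUC with 0.70 the determination of success, leaves inconclusive diagnoses out of the ROC curve, and sets the threshold for the next study on the entire group. No analysis by prior diagnosis is planned.

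**The concern.** A patient with long-standing epilepsy, an outside EEG and a settled diagnosis, who moves to the Center for treatment, meets Section 3.2.1, meets no exclusion in Section 3.3.1, appears on the lists in Section 3.4 and can satisfy the count in Section 7.1. The same holds for a patient already diagnosed elsewhere with non-epileptic events. Neither is clearly in the Method 1a population.

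The introduction says the test is meant to help clinicians start treatment or redirect a workup, which presupposes an open diagnosis. If settled cases are mixed in, the AUC that decides success and the threshold carried forward may describe a different case mix from the one Aim 1 concerns. With no breakdown by prior diagnosis planned, the final report would not show it.

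**Working it through.** **1. The plan's own figures.** Inputs from Sections 7.1 and 7.2: N = 240, split 50/30/20, AUC 0.87 against 0.70, alpha 0.05, power 0.80, 68 per group.

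- Planned groups: 0.50 × 240 = 120 epilepsy, 0.30 × 240 = 72 non-epileptic, 0.20 × 240 = 48 unknown. The smaller group, 72, clears 68.
- The Hanley–McNeil variance of an AUC A with m cases and n non-cases is V(A) = [A(1−A) + (m−1)(Q₁−A²) + (n−1)(Q₂−A²)]/(mn), with Q₁ = A/(2−A) and Q₂ = 2A²/(1+A). At 68 per group, V(0.70) = 0.00200 and V(0.87) = 0.00098.
- Two independent AUCs, two-sided: 1.96√(2 × 0.00200) + 0.842√(0.00200 + 0.00098) = 0.170, which equals 0.87 − 0.70. This reproduces 68.
- One AUC against a fixed 0.70, which is the test as worded, needs only 31 per group. So 68 is conservative for the test described.

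**2. Effect on the AUC.** Let f be the share of the epilepsy arm with established disease, with one common non-epileptic group. Then

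pooled AUC = f × AUC(established) + (1 − f) × AUC(undiagnosed).

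The documents give neither f nor the AUC in established cases, so both are assumed over a range. AUC(undiagnosed) is set at the null, 0.70. Chances of success come from simulation: 120 v 72, normal markers, DeLong standard error, two-sided 5%, success in the upper tail. Ranges show the spread between repeated runs.

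| AUC in established cases | f = 25%: pooled AUC | f = 25%: success | f = 50%: pooled AUC | f = 50%: success |
|---|---|---|---|---|
| 0.60 | 0.675 | about 1% | 0.650 | under 1% |
| 0.70 | 0.700 | 3–4% | 0.700 | about 4% |
| 0.87 | 0.743 | 23–25% | 0.785 | 70–72% |
| 0.95 | 0.763 | 45–47% | 0.825 | 98% |

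With no established cases the rate is 3–4%.

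**3. The opposite error.** Suppose AUC(undiagnosed) = 0.87, AUC(established) = 0.60, and a fraction k of all 240 arrives with established epilepsy while the rest follow 50/30/20. At k = 20% there are 48 established cases among 48 + 0.5 × 192 = 144 with epilepsy, so f = 1/3 and the pooled AUC is 0.87 × 2/3 + 0.60 × 1/3 = 0.78. With the Hanley–McNeil variance the chance of success is then about 57%, against nearly 100% with no established cases. A test that works in the intended patients could fail.

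**4. Effect on group size.** Under the same intake the non-epileptic group is 0.30 × 240 × (1 − k) = 72(1 − k): 64.8 at k = 10%, 57.6 at 20%, 50.4 at 30%. It falls below 68 once k exceeds 1 − 68/72 = 5.6%, or about 13 patients. By step 1 this breaks the plan's stated requirement but is not in itself a loss of power: if the AUC is 0.87 in every case, power stays above 99% for k up to 50%.

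**The case against.** The strongest reply is that the restriction already exists. Method 1a is the Aim 1 definition, Section 3.2.1 is shared eligibility for all aims, and in Method 1a the outside-site allowance belongs to the workup that follows referral, so an old outside EEG alone would not qualify. This stands in part. The point is an unreconciled conflict, not a missing restriction. But Section 7.1 also describes the Aim 1 count and does not repeat the restriction, and screeners will work from Sections 3.2.1 and 3.4.

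A reader might infer that established epilepsy supplies easy true positives to the epilepsy arm only, so that the AUC is inflated. The documents do not support that. A confident panel diagnosis concerns the reference label, not the CARPE value. Nothing shows that CARPE separates established epilepsy better than new epilepsy. The Aim 3 hypothesis that accuracy falls with time since the last event, and the Aim 4 hypothesis that levels distinguish seizure-free patients, both allow the reverse. Settled non-epileptic cases can enter the other arm as well.

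It can also be said that wide intake is deliberate. Section 3.4 aims at a true cohort, and the introduction says about 30% of patients treated for epilepsy have another cause, so a prior label does not close the question. The second part stands and shapes the fix. The first does not answer the point: consecutive enrolment guards against selection within a population but does not say which population is meant.

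**Conclusion.** The conflict between Method 1a and Sections 3.2.1, 3.3.1, 3.4 and 7.1 is plain on the text, and it reaches both the analysis that decides success and the threshold. The result may not describe the patients Aim 1 concerns. The direction is not known. Under the assumed values, a quarter of the epilepsy arm being established moves the chance of declaring success from 3–4% to anywhere between about 1% and 47%. There is no bias if CARPE performs equally in established and new cases. The shares and the AUCs in established cases are illustrations; 0.87 is the pilot sICAM5 figure, not an estimate for established disease. The conclusion that success would be falsely declared goes further than the documents allow. This should be corrected because the change is cheap and uses the protocol's own definition.

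**What to change.** For the Aim 1 outpatient route, carry the Method 1a restriction into Sections 3.2.1, 3.4 and 7.1: the diagnosis of the events is in question at referral, and the workup, including the EEG, follows referral. Define it by the referral question rather than by prior label or treatment, so that treated patients sent for diagnostic clarification stay in.

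If intake stays broad, code the referral question and any prior outside diagnosis (epileptic or non-epileptic) from the chart at enrolment, blind to CARPE and before the panel review. Base the deciding AUC and the threshold on the subset with an open diagnostic question, and report the full cohort as a sensitivity analysis.

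The cost is a wording amendment, or one or two extra fields from charts that Section 6.1 already has abstracted. Coding the referral question needs some judgement, so the rule should be written down beforehand. Some new referrals would no longer count toward the 240, or the deciding subset could fall below the stated 68 per group. In simulation, 60 v 50 still gives about 99% power for an AUC of 0.87 against 0.70.

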3.2.2 Control Subjects

- Aged 18 and older
- Provide verbal confirmation that they do not experience seizures or suspected seizures of any type (a single instance of febrile seizure prior to age 2 is allowed)
- Provide verbal confirmation that they have not taken any medications used to treat seizures for a minimum of two months prior to providing a blood sample
- Able to provide Informed Consent

3.3 **Exclusion Criteria**

